8.2 The project duration

This project is planned to be completed within two years, with recruitment to start in February 2024 after the ethics approval. This timeline is inclusive of all aspects of the research project.

8.3 Any participant follow-up

There is no planned follow up following the cessation of the study.

Participants will be provided with a copy of the research report after publication if this option is selected on the consent form

Please ensure your responses to Sections 9-12 comply with Deakin's Research Data Management procedure and accurately reflect the details you have included in your Research Data Management Plan (a compulsory document for all Deakin research).

9. Data Collection/Gathering:

9.1 What information are you going to collect/gather/generate? (as required in addition to that outlined in the HREA)

Please note that prior to the recruitment of the first participant, this clinical trial is to be registered within the ANZCTR.

Personal information

- Name

-Contact number

- Email address (to be sent electronic PLS and consent form, and if selected, publication of study)

Screening measures

- Participant age
- Habitual dietary intake prior to the intervention
- Sleep quality via PSQI questionnaire
- Dietary allergies

-Chronotype measures via morningness eveningness questionnaire (MEQ)

Outcome measures

- Biochemical measures (plasma amino acids and plasma melatonin)
- Palatability of ALAC supplement doses via VAS-GI symptoms questionnaire administered

-Preference of the ALAC supplement doses via VAS -sensory evaluation questionnaire administered

Data Collection

- Blood samples across five timepoints during each intervention session on each of the four separate lab visits i.e., all four supplement doses, to be collected.

-Saliva sample at two time points during each intervention session, on four separate occasions i.e., all four supplement doses to be collected.

9.2 Data collection/gathering techniques: How will you collect/gather the information? Will any third parties be involved in any aspects of recruitment or data collection?

Screening measures

Participant characteristics – age, training level, medication use, alcohol and caffeine consumption, travel history across time zones, recency of night shift work will be collected at baseline using a simple questionnaire (Appendix 1).

Sleep quality – Participants will be screened using the Pittsburgh Sleep Quality Index (Appendix 2) to ensure the participants do not face any pre-existing sleeping difficulties.

Diet Recall - Participants will be asked to record a 3 day diet recall using Easy Diet Diary (EDD) mobile app prior to their first lab visit.

Outcome measures

Biochemical measures – Blood samples will be collected by a researcher with phlebotomy training across five-timepoints on each intervention day. Plasma amino acid analysis will then be completed at Deakin University through liquid chromatography triple-quadrupole mass-spectrometry.

Plasma melatonin will be assessed through enzyme-linked immunosorbent assay according to manufacturer's instructions.

Palatability and preference will be assessed through a validated VAS -GI symptoms and VAS- sensory evaluation questionnaire to gauge the palatability and acceptance of the different supplement doses.

9.3 Impact of and response to participant withdrawal

Participants will be informed about their right to withdraw from the study at any time, which will not jeopardise their relationship with the research team or Deakin University.

Data collected from a participant selecting to withdraw from the study will only be destroyed if this is requested (optional tick box on the withdrawal of consent form), otherwise all collected data will be retained for research integrity purposes.

Forms will be returned to a member of the research team, who will review the withdrawal form and store this within a locked filing cabinet.

If the number of participants that withdraw themselves from the study impacts the sample size required (n=16) then recruitment will continue in order to reach this sample size

10. Data Management:

10.1 How will you store, provide access to, disclose, use/re-use, transfer, destroy or archive the information that you collect/gather? (as required in addition to that outlined in the HREA)

Digital and hard copies of data will be collected throughout this research. Digital data will be stored using the software sharing program 'Syncplicity', which is a secure program that is regularly backed up. Only the research team listed will have access to this data. Physical copies of data will be stored in a private lockable filing cabinet in an area of the Deakin University campus that requires security clearance to access.

Each participant will be allocated a unique study ID code. These ID codes will be linked to the participant names and stored within a spreadsheet. This spreadsheet linking participants to an ID code will be stored on this same network drive, which will only be accessible to the research team.

During the study, blood samples will be stored in -80 degree Celsius freezers in the level 2 analytical laboratories of building J at the Burwood campus. These laboratories are limited to swipe access only.

Collected data will be archived and stored for a period of 15 years following publication of results from this study. Following this 15-year period, data will be destroyed. All sensitive data contained as a physical copy will be shredded, any electronic data will be permanently deleted, and blood samples will be destroyed.

Include a Research Data Management Plan in accordance with National Statement 3.1.45 and 3.1.56 and Deakin's Research Data Management procedure.

11. Data Analysis:

11.1 How will you measure, manipulate and/or analyse the information that you collect/gather?

Initially, data cleaning will be performed to identify missing and corrupt data. Data will be analysed using generalised linear mixed models within StataIC 16 (StataCorp LLC, TX, USA). The effect of dietary intervention (dose response effect of α -lactalbumin) and time period (i.e., sequence receiving condition) and their interaction, will be fitted as fixed effects to determine whether there was a difference in the effect of dietary intervention over period on dependant variables of amino acid analysis and plasma melatonin. Participant identification number will be used as a random factor to account for repeated measures in each model.

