4.3 The research questions/aims/objectives/hypothesis

Research Question: What is the optimal dosage and timing of evening alpha-lactalbumin supplementation to increase the serum TRP:LNAA ratio?

Aim: To identify the optimal dosage of evening alpha-lactalbumin supplementation required to increase the serum TRP:LNAA ratio in healthy active population.

Objectives:

a) To study the dose response of 4 different doses i.e. 10, 20, 30, 40 g of ALAC supplementation on the TRP:LNAA ratio.

b) To observe the difference between the serum melatonin levels 3 hrs post consumption of 4 different ALAC dosages.

c) To test the palatability and appetite post 4 different dosages of ALAC supplementation.

Hypothesis:

1. There will be linear relationship between increasing ALAC dosages and serum TRP:LNAA ratio before reaching a plateau at ~40g.

2. Higher doses of ALAC will increase TRP:LNAA ratio for a longer time period

3. The palatability, appetite and preference will reduce at higher ALAC doses

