Participants will be required to report to the university at 17:00 hrs with a fasting period 2.5 hrs before arrival (14:30 hrs). Upon their arrival, simple height and weight measures will be taken by the researchers. Within the first hour of arrival, a trained researcher will insert a cannula into a forearm vein of the participants for blood samples to be taken. Baseline blood and saliva samples will be collected before the experimental supplement consumption. Further, each participant will be provided the experimental ALAC protein shake and a Visual Analog Scale (VAS) -sensory evaluation questionnaire to assess the preference of the ALAC shake at immediately post consumption of the drink (T=0 mins). Participants will also complete a Visual Analog Scale VAS -GI symptoms questionnaire, at two time points i.e. baseline (T=0 mins) and 2hrs post supplement consumption i.e. (T= 120 mins). Small amounts of blood will be drawn (5 mL) at half an hour interval from the time of the supplement consumption (pre supplement and 90 mins, 120 mins, 180 mins and 210 mins post supplement). During the experimental protocol, from T=0 to T= 210 mins, the participants will be asked to relax in an environment consistent lighting and discouraged from using screens. A saliva swab collection will once again be repeated at 3 hrs (210 mins) post supplement consumption. A simple chronotype questionnaire will also be administered to all the participants at this stage. At the end of the study protocol i.e., **21:00hrs**, the participants will be screened for alertness via Karolinska Sleepiness Scale (KSS)(Appendix 4) to assess their ability to drive back home post the intervention and in the event a participant scores >6.8 on the KSS scale, alternate arrangements to travel back home or temporary sleeping arrangements at Deakin University Campus will be made to ensure the participant's safety. Participants will also be handed a boxed dinner meal before leaving the lab. This procedure will be replicated for each of the four visits made be every participant, during the intervention. Participants will also receive a reimbursement via \$100 gift card on successfully completing all 4 intervention sessions.

Wash-out

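### The only time term in the section 11.1 model is visit order, so the timing question and hypothesis 2 have no stated analysis

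*Protocol*

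**What the plan says.** **The questions (protocol 4.3).** The research question is "What is the optimal dosage and timing of evening alpha-lactalbumin supplementation to increase the serum TRP:LNAA ratio". Hypothesis 2 reads "Higher doses of ALAC will increase TRP:LNAA ratio for a longer time period". Objective (a) concerns dose only: "To study the dose response of 4 different doses i.e. 10, 20, 30, 40 g of ALAC supplementation on the TRP:LNAA ratio".

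**The data (8.1, 9.1, 9.2).** Each participant attends four visits, one dose per visit. Section 9.1 plans "Blood samples across five timepoints during each intervention session on each of the four separate lab visits". Section 8.1 lists the times as "pre supplement and 90 mins, 120 mins, 180 mins and 210 mins post supplement", that is, one pre-dose and four post-dose samples.

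**The model (11.1).** A generalised linear mixed model has dose as a fixed effect, and "time period (i.e., sequence receiving condition) and their interaction, will be fitted as fixed effects". The stated purpose of the interaction is to see whether the dose effect differs over period. For the random part: "Participant identification number will be used as a random factor to account for repeated measures in each model". Nothing in the protocol names sampling time, a dose by sampling-time term, a visit-level effect, a within-visit covariance, or a visit summary such as area under the curve, peak or time above baseline. The pre-dose sample has no stated role in the analysis.

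**The concern.** The clock schedule in 8.1 is the same at every visit. Timing can therefore be learned only from minutes after the drink, which is what the repeated samples supply. The model does not use them that way: its time term is defined in parentheses as the sequence of conditions. Followed as written, no output shows how the ratio, or the dose effect on it, changes between 90 and 210 minutes. Half of the research question and one of three hypotheses have no analysis. The choice among peak, area or duration would then be made after the data are seen.

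A second problem is conditional. Dose is assigned per visit, but the only random factor is participant. If every sample enters one model, the dose test draws its error term from samples rather than from visits, and the pre-dose sample is averaged into the dose effect.

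**Working it through.** The protocol gives no figure on this point. The power statement in 11.4 does not involve sampling time and is not used here.

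**1. Questions against terms**

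| Question | Term needed | In 11.1? |
|---|---|---|
| Dose response | dose | yes |
| Timing after the dose | sampling time, or a timing summary | no |
| Longer rise at higher dose (hypothesis 2) | dose effect at late times, or a duration summary | no |
| Order of visits | period | yes, labelled as time |

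If the authors meant sampling time, the definition in parentheses is wrong and the crossover period then drops out of the model. The paragraph needs rewriting on either reading.

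**2. Counts.** 16 participants × 4 visits = 64 visits. Samples: 64 × 5 = 320, or 64 × 4 = 256 post-dose only.

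Error degrees of freedom for dose, with dose, period and participant fitted:
- five samples: 320 − 1 − 15 − 3 − 3 = 298
- four samples: 256 − 22 = 234
- visit level: 64 − 22 = 42

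**3. Dilution, if all five samples enter.** Let Δ be the post-dose difference between two doses, with no difference before dosing. The fitted contrast is (0 + 4Δ)/5 = 0.8Δ, a loss of 20%.

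**4. Clustering, with sampling time added but no visit term.** Let ρ be the share of within-participant variance common to one visit. The protocol does not give ρ, so a range is shown. This case uses four post-dose samples and no true dose effect.

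For a single contrast, the visit-level mean square has expectation 1 + 3ρ on 42 df, and the within-visit mean square 1 − ρ on 192 − 3 = 189 df. The pooled error is [42(1 + 3ρ) + 189(1 − ρ)]/231 = 1 − 0.273ρ. The variance is therefore understated by R = (1 + 3ρ)/(1 − 0.273ρ), and a nominal 5% test rejects with probability of about 2[1 − Φ(1.96/√R)].

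| ρ | R | Single contrast, formula | Single contrast, simulated | Three-df dose F test, simulated |
|---|---|---|---|---|
| 0.1 | 1.34 | 9% | about 10% | about 12% |
| 0.2 | 1.69 | 13% | about 14% | about 20% |
| 0.3 | 2.07 | 17% | about 19% | about 30% |
| 0.5 | 2.89 | 25% | about 25% | about 44% |

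The formula and the simulation agree within two percentage points. With the visit level modelled, the simulated rate returned to 4.3–5.4%.

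**5. The fixed effects as written, five samples, no sampling time.** A post-dose rise that is not modelled stays in the residual and works against the clustering. A flat rise of s within-participant SDs in four of five samples adds a sum of squares of 5 × (1/5)(4/5) × s² = 0.8s² per visit, or 51.2s² over 64 visits. The residual df are about 292: 298 less the 6 dose-by-period df that a four-sequence Latin square can estimate within participants. The residual variance therefore rises by about 51.2s²/292 = 0.175s², which is 0.70 at s = 2 and 1.58 at s = 3, against a base of about 1.

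Simulated rejection of a nominal 5% dose F test under no dose effect (participant fitted as fixed):

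| Rise (SDs) | ρ = 0.1 | 0.2 | 0.3 | 0.5 |
|---|---|---|---|---|
| 0 | 15% | 27% | 36% | 53% |
| 2 | 2% | 7% | 14% | 28% |
| 3 | 0.1% | 1% | 3% | 10% |

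The test can be far too liberal or far too conservative. Which one depends on two quantities that the protocol does not supply.

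**The case against.** The strongest reply is that 11.1 never says all samples of a visit enter one model. It lists several dependent variables and refers to each model. If one value per visit is analysed, then dose, period and a random participant effect form a standard crossover model, and the dilution and clustering disappear. The analysed value, the role of baseline and the covariance structure are often left to a statistical analysis plan. This stands, and it makes steps 3 to 5 conditional. It does not rescue the timing question: the protocol names no such value, and it defines its time term as visit order.

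A reader might also infer two stronger claims that the document does not support. One is that the model treats samples of one visit as independent. It does not: a participant effect correlates them, but only as strongly as samples from different visits. The other is that standard errors for dose must be too small. That holds when sampling time is fitted or negligible. With the fixed effects as written, a large rise after the dose can push the error rate below 1%.

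Finally, the stated aim and objectives (a) to (c) concern dose, serum melatonin and palatability, so timing is not the whole study. It is nevertheless in the research question, in hypothesis 2 and in the expected outcome in 4.4.

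**Conclusion.** The point holds for the model as stated. Section 11.1 has no term or summary for time after the dose, so the timing half of the research question and hypothesis 2 have no analysis. This follows from the text alone and needs no assumption. It is a model fixed wrongly in the protocol, not a detail left for later.

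The harm to the dose test is conditional on all samples of a visit entering one model. In that case the dose contrast is diluted to 4/5, given equal pre-dose means, and the type I error is uncontrolled. The rates in steps 4 and 5 rest on an assumed visit share of 0.1 to 0.5 and, in step 5, an assumed rise of 0 to 3 SDs. They show the possible range and do not forecast this trial.

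**What to change.** Rewrite 11.1 before analysis as a linear mixed model on the post-dose values:

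- Covariate: that visit's pre-dose value.
- Fixed effects: dose, categorical sampling time, dose by sampling time, and visit period as a separate main effect.
- Random effects: participant and visit within participant. An unstructured or continuous-time within-visit covariance would also serve. The listed gaps are unequal (90 to 120, 120 to 180, 180 to 210 minutes), so a plain equal-spacing autoregressive form does not suit.
- Hypothesis 2: pre-specify dose contrasts at 180 and 210 minutes, or a defined duration summary. The dose by time interaction alone shows only that profiles differ, and a higher peak would produce that too.

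For the dose question, an acceptable alternative is one baseline-corrected value per visit, such as incremental area under the curve, with dose, period and random participant. That gives 64 values and needs no visit-level term. Because 11.3 rules out substituting missing values, this route also needs a rule for visits with a missing sample.

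The cost is one rewritten paragraph, slightly more analysis work and possibly wider intervals. No new data are needed.

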6.2 The rationale for choices of method/s (tied to project aims/objectives)

Double blinding ensures that both the research team and participants are unaware of the treatment dosages throughout the intervention, minimising the risk of bias. The crossover design allows for the participants to act as their own controls, thus limiting confounding influences of across subject variability. Assigning participants dosages via a latin square design model reduces the carryover effects from other within subject variables such as gender and other confounding variables and ensures proper balance such that the sequencing of experimental conditions does not affect outcomes of the trial.

7. The participants including:

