Participants will be randomly allocated a single dose of the α -lactalbumin (BiPRO Alpha 9000; Agropur Inc, Appleton, WI), in a crossover design (each participant will complete all 4 doses on 4 different occasions) on their scheduled lab visit dates. A latin square design will be used for a counterbalanced randomisation of the dosages to the participants to avoid any potential carryover effects or within participant variability. To blind both participants and the research team, the experimental drinks will be matched for taste and provided to the participants by an external researcher. The latin square model will ensure adequate sequencing of the dosages across at the participants to avoid within subject variability.

Intervention

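### The analysis section equates visit period with sequence and puts their interaction with dose in the main model, and the protocol credits a Latin square with avoiding carryover, which it cannot do

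*Protocol*

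**What the plan says.** Section 11.1 plans a generalised linear mixed model with dose, "time period (i.e., sequence receiving condition) and their interaction, will be fitted as fixed effects". The same sentence gives the purpose of the interaction: "and their interaction, will be fitted as fixed effects to determine whether there was a difference in the effect of dietary intervention over period". Participant is the only random term: "Participant identification number will be used as a random factor to account for repeated measures in each model". No term for the previous dose is planned.

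On the design, section 8.1 states that "each participant will complete all 4 doses on 4 different occasions" and that "A latin square design will be used for a counterbalanced randomisation of the dosages to the participants to avoid any potential carryover effects". Section 6.2 adds that the Latin square "reduces the carryover effects from other within subject variables such as gender and other confounding variables". It further claims that the square "ensures proper balance such that the sequencing of experimental conditions does not affect outcomes of the trial". Neither section says which Latin square is meant. Separately, sections 6.1 and 8.1 set a washout of at least 3 days. Section 8.1 gives its purpose as limiting carryover and cites literature on gaps of 1-3 days.

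**The concern.** There are three linked problems with how order is handled.

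- **Two factors under one name.** Visit number (1-4) and sequence (the order group to which a participant is allocated) are different factors, and section 11.1 defines one as the other. Two analysts could fit two different models from the same sentence, and one of those models does not adjust for visit.
- **An interaction in the main model.** Once dose-by-period is in the model, the dose coefficients that software prints under reference coding are effects at one visit only. They are not the paired comparison for which the crossover was chosen and on which section 11.4 bases its power. The section does not say which contrast will be reported.
- **A property that the design does not have.** A Latin square balances dose against visit. It does not stop one dose from affecting the next visit, and unless it is of Williams type it does not balance which dose precedes which. Sex, named in section 6.2, is neither a within-participant variable nor a source of carryover.

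At stake are the clarity and precision of the primary dose contrasts for the TRP:LNAA ratio, and the cost of adjusting for carryover should that prove necessary.

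**Working it through.** **Inputs.** From the protocol: 4 doses, 4 visits and 16 participants (7.1, 8.1), and a root within mean square error of 0.05 (11.4), taken here as the within-participant SD. Assumed: one replicated 4x4 square with 4 participants per sequence, one outcome value per visit, and a between-participant variance share (ICC) of 0.3, 0.5 or 0.7, because the protocol gives none.

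**The plan's own figure.** Section 11.4 states 85% power. A paired test with n = 16, difference 0.024 and two-sided alpha 0.01 gives 19.4% if 0.05 is the SD of the difference, and 8.7% if that SD is √2 × 0.05. So 85% is not reproduced. That is a separate matter: only the value 0.05 is used here, and it cancels from every ratio below.

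**1. Additive model, dose + visit.** SE of a dose contrast = √(2 × 0.05² / 16) = √0.0003125 = 0.0177. Residual df within participants: 64 − 16 − 3 − 3 = 42.

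**2. Adding dose-by-visit (9 df).** In one 4x4 square, dose and visit together identify the sequence, so adding sequence to this model does not raise its rank (16 either way). Three of the 9 df are therefore sequence, a between-participant comparison. The other 6 come from the within-participant residual: 42 − 6 = 36. The dose contrast averaged over visits keeps SE 0.0177. The two-sided 0.01 critical t moves from 2.698 to 2.719, and power changes by under half a point.

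**3. Dose contrast at one reference visit.** This compares 4 participants with 4 others. Variance = 2(σ²_b + σ²_w)/4, with σ²_b + σ²_w = 0.0025/(1 − ICC). The ratio to step 1 is √(4/(1 − ICC)).

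| ICC (assumed) | SE at one visit | Ratio to 0.0177 |
|---|---|---|
| 0.3 | 0.0423 | 2.4 |
| 0.5 | 0.0500 | 2.8 |
| 0.7 | 0.0645 | 3.7 |

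**4. If sequence is fitted literally.** There is no visit main effect, and visit differences are absorbed into dose-by-sequence. The reference-coded dose coefficient is then a within-participant contrast in the 4 members of one sequence: √(2 × 0.0025/4) = 0.0354, a ratio of 2.0 at any ICC.

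**5. What the square does about carryover.** In a cyclic square each dose, when preceded by another, always follows the same one (3 times out of 3). In a Williams square each ordered pair occurs once. Adding a first-order carryover term for previous dose leaves every dose contrast estimable in both:

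- cyclic: SE rises from 0.0177 to between 0.035 (ICC 0) and 0.041 (ICC 0.8);
- Williams: SE is about 0.0185.

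**6. Bias if carryover exists and is not modelled.** Let c be the carryover per 10 g of the previous dose. The mean carryover falling on 10, 20, 30 and 40 g is 3c, 0.75c, 1.5c and 2.25c in the cyclic square, and 2.25c, 2c, 1.75c and 1.5c in the Williams square. The bias against 10 g follows by subtraction.

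| Contrast | Cyclic | Williams |
|---|---|---|
| 20 − 10 g | −2.25c | −0.25c |
| 30 − 10 g | −1.5c | −0.5c |
| 40 − 10 g | −0.75c | −0.75c |

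The protocol gives no basis for a value of c.

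**The case against.** The strongest reply is that these are loose words rather than faulty methods.

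- **The interaction.** A reader might infer that it throws away the crossover's precision. It does not. Visit-averaged contrasts keep SE 0.0177, section 11.1 gives the interaction a purpose of its own, and the choice of reported contrast may sit in an analysis plan that is not shown. This stands. The larger standard errors are a risk only if reference-coded coefficients are taken as the dose effect.
- **The gloss.** It could mean the order position in which a dose is received, which is visit number. That is possible, but the words name sequence, and the reader should not have to choose.
- **The square.** A four-treatment Williams square is itself a Latin square, so the text is compatible with one. This stands: cyclic is a worst case, not what the protocol says.
- **Confounding.** A reader might infer that carryover would be fully confounded with dose. It would not, because even the cyclic square leaves the contrasts estimable, at an SE of about 0.041.
- **The washout.** A gap of at least 3 days, with a blood sample before the supplement at each visit, is the working protection and may bring c close to zero. This stands, and a Williams square gives no gain in unadjusted bias on 40 versus 10 g. But it makes the washout the source of protection and does not make the claims for the square correct.

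**Conclusion.** The point holds in limited form. Section 11.1 names one factor and defines it as another; read literally, it omits the visit main effect. The dose-by-period term does not belong in the main model: three of its nine df are sequence, and it invites a reading of the dose coefficients with an SE 2.4 to 3.7 times larger (2.0 if sequence is fitted). It does not harm the visit-averaged contrasts beyond 6 residual df. Sections 6.2 and 8.1 credit the Latin square with protection against carryover that it cannot give. If the square were cyclic, adjusting for carryover would raise the SE from 0.0177 to about 0.041, against about 0.0185 in a Williams square.

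These sizes rest on one replicated square with 4 participants per sequence, one value per visit, and 0.05 as the within-participant SD. The ratios of 2.4 to 3.7 also rest on an ICC between 0.3 and 0.7. Nothing in the protocol shows that carryover will occur or that a cyclic square will be used. The change is worth making because it costs almost nothing and the allocation cannot be altered once dosing has begun.

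**What to change.** - **Section 11.1:** define visit number (1-4) and sequence as separate factors. Make the primary model dose plus visit number as additive fixed effects with random participant. State that dose contrasts are reported averaged over visits. Move the dose-by-visit interaction and a previous-dose term to sensitivity analyses.
- **Section 8.1:** name the design as a four-sequence Williams square with 4 participants per sequence.
- **Sections 6.2 and 8.1:** attribute carryover control to the washout, and to the square only the balance of dose over visits and of preceding doses. Delete the reference to sex as a carryover source.

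The cost is wording and a new allocation list, set before the first visit. The number of participants, the number of visits and the measurements are unchanged.
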